5.2.5.4 Physical examinations

Weight and BMI will be presented at each visit with raw value and change from baseline (Statistical tables 14.3.20.1 & 14.3.20.2). Number of normal, Abnormal CS/N, Abnormal CS/AE, Abnormal NCS values will be presented at each visit by body systems for each treatment group (Statistical table 14.3.19).

All individual measurements will be provided in Listing 16.2.9.

5.2.5.1 Vital signs

Quantitative descriptive statistics will be tabulated for each vital sign recorded (heart rate, temperature, systolic and diastolic blood pressure) at each time over the course of the study (e.g., at each timepoint for each visit) for raw values and change from baseline (Statistical tables 14.3.22.1 & 14.3.22.2)

All individual measurements will be provided in Listing 16.2.10.

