12.4 Emergency Medication

The possibility that IFN-K can cause anaphylaxis in humans cannot be excluded. All participating centers should therefore be equipped to manage cardiovascular resuscitation with adequate material ready for use at the time of study product administration and during the 1 hour observation period after each administration.

Please refer to Section 10.2.2 for emergency unblinding and contact details of Neovacs SA's Clinical Safety Physician and Delegate Medical Monitor.

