ACR = American College of Rheumatology; ACS = American Cancer Society; AE = Adverse event; ANA = Anti-nuclear antibodies; BILAG = British Isles lupus assessment group; CLAS = Cutaneous lupus erythematosus disease area and severity index; CRP = C-reactive protein; CS = corticosteroids; DNA = Deoxyribonucleic acid; ECG = Electrocardiogram; FACIT = Functional assessment of chronic illness therapy; IFN = Interferon; KLH = Keyhole limpet hemocyanin; PGA = Physician's global assessment; RT qPCR = Reverse transcription quantitative polymerase chain reaction; SELENA = Safety of estrogen in lupus erythematosus national assessment; SF-36 = Short form-36 questionnaire; SLE = Systemic lupus erythematosus; SLEDAI = SLE disease activity index; SLICC = System Lupus International Collaborating Clinics; VAS = Visual analog scale.

¹ Including body temperature, weight and height; height being measured only during screening.

² Including examination of the cervix, and detection of high risk HPV (by RT qPCR) on PAP smear; unless performed and documented 3 months prior to the first planned study product administration.

³ Vital signs include brachial pulse and blood pressure. They will be performed after patient has been in a supine position for 3 minutes. At Visits 2, 3, 4, 6 and 9, vital signs will be performed prior to and 1 hour post study product administration.

Confidential

Statistical Analysis Plan

Study Name: IFN-K-002

SAP version & date: v4, 18/Jun/2018

⁴ 240 mcg study product administration at Visit 2, 3 and 4. 120 mcg study product administration at Visit 6 and 9.

⁵ Blood samples are to be taken prior to administration of the study product, when applicable.

- Complete means Hemoglobin, complete blood cell count and differential (Red Blood Cells, White Blood Cells, Neutrophil, Lymphocyte, Platelet), INR, PT, PTT, fibrinogen, serum Urea, serum Albumine, serum creatinine level, serum Total protein, Creatinine clearance GFR, Serum Alanine Aminotransferase, Aspartate Aminotransferase, Alkaline Phosphatase, Coombs test, Circulating Anti-Coagulant, Creatine Phospho Kinase. CD19 counts will be performed at Visit 2.
- Disease oriented means Hemoglobin, complete blood cell count and differential (Red Blood Cells, White Blood Cells, Neutrophil, Lymphocyte, Platelet), INR, PT, PTT, fibrinogen, serum Urea, serum Albumine, serum creatinine level, serum Total protein, Creatinine clearance GFR, Coombs test, Circulating Anti-Coagulant, Creatine Phospho Kinase

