4.2.3.2 Vital signs

Vital signs are evaluated during each visit. Vital signs include brachial pulse rate and systolic and diastolic blood pressures. These recordings are made after at least 3 minutes of rest, measured in the supine position. Recordings are made prior to and 1-hour post study product administration, when applicable.

Safety will be based at each visit on raw value and change from baseline.

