5.4 Data handling conventions

5.4.1 Baseline definitions

For IFN gene signature, only Week 0 (visit 2) will be considered as baseline.

For BILAG scores, a baseline value will be defined for each body system. This baseline will be the value at Week 0 (visit 2).

For other efficacy and safety endpoints the last observation prior to the first dose of study treatment administration will be used as the baseline value. This will usually correspond to the measurement performed at Week 0 before first-dose. However, in case of missing value at Week 0, the last available value recorded during screening will be used as baseline value.

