7.3 Adverse events

Analysis of solicited local & systemic reactions 1-hour post study product administration was planned in the protocol. Time of these AEs was not recorded into the eCRF. This analysis will not be done.

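### One-hour vital signs after doses 2 to 5 are differenced from Week 0 instead of the same-visit pre-dose value, so the acute change is poorly summarised

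*SAP*

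**What the plan says.** **When vital signs are taken.** The schedule in SAP 2.3.3 states: "At Visits 2, 3, 4, 6 and 9, vital signs will be performed prior to and 1 hour post study product administration". Those visits are Weeks 0, 1, 4, 12 and 24, the five dosing visits. SAP 4.2.3.2 repeats it: "Recordings are made prior to and 1-hour post study product administration, when applicable".

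**What is summarised.** SAP 4.2.3.2 defines the endpoint: "Safety will be based at each visit on raw value and change from baseline". SAP 5.2.5.1 (Vital signs) plans quantitative descriptive statistics "at each time over the course of the study (e.g., at each timepoint for each visit) for raw values and change from baseline". The table list in SAP 10.1 has two vital-sign tables, 14.3.22.1 (values) and 14.3.22.2 (change from baseline). Individual measurements go to Listing 16.2.10.

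**Which baseline applies.** SAP 5.4.1 makes exceptions for the IFN gene signature and BILAG. For all other efficacy and safety endpoints, "the last observation prior to the first dose of study treatment administration will be used as the baseline value". It adds that "in case of missing value at Week 0, the last available value recorded during screening will be used as baseline value". SAP section 9 derives change as the value at a visit minus that one baseline. No same-visit difference is defined anywhere.

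**One-hour reactions.** Protocol 13.4 lists solicited local and solicited systemic reactions at one hour as safety endpoints. SAP 7.3 removes their analysis: "Time of these AEs was not recorded into the eCRF. This analysis will not be done". The SAP keeps solicited reactions over seven days after each dose, with the injection day included, and adverse events by dose period.

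**The concern.** A pre-dose and a one-hour reading at the same visit form a pair whose purpose is to show what the injection did. Protocol 12.4 gives the reason to look: "The possibility that IFN-K can cause anaphylaxis in humans cannot be excluded". Protocol 11.3 requires at least an hour of observation after each dose.

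The single baseline separates the two halves of that pair at four of the five doses. At Week 24, for example, the tabulated one-hour change is the acute effect plus 24 weeks of change in disease and background treatment, including the corticosteroid taper in Table 4 of the protocol.

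An acute fall in a few patients would show mainly in the spread and tail of the paired differences, and neither is tabulated. Laboratory, physical examination and ECG results are also counted by clinical-significance category; vital signs get quantitative statistics only. With the one-hour reaction analysis removed, vital signs are the only one-hour assessment that still has a planned table.

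**Working it through.** The plan states no figure for vital signs, so there is nothing to reproduce. The check traces the definitions and then sizes the effect under stated assumptions.

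**1. What the tabulated change contains.** Write W0 for the Week 0 pre-dose value, and pre and post for the pre-dose and one-hour values at a later dosing visit. Then

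post − W0 = (post − pre) + (pre − W0).

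The first term is the acute change and the second is drift since Week 0. At dose 1, pre is W0, so the drift term is zero and the existing table already gives the same-visit change. The issue is confined to doses 2 to 5.

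**2. What can be recovered from the planned tables.** If both timepoints are tabulated, as SAP 5.2.5.1 indicates, and pairs are complete,

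mean(post − W0) − mean(pre − W0) = mean(post − pre).

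So the mean acute change is recoverable. Its spread is not:

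Var(post − pre) = Var(post) + Var(pre) − 2 Cov(pre, post).

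The planned tables give the two variances but no covariance of pre with post. The paired SD, the confidence interval, the quartiles of the difference and the count of large shifts can be obtained only by going to Listing 16.2.10.

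A simulated set of 89 patients with invented values (downward drift built in, followed by an acute rise) shows both facts. The difference between the two mean changes from Week 0 was 2.15, equal to the mean same-visit change of 2.15. The tabulated one-hour change from Week 0 had mean −2.30 and SD 9.73, while the same-visit change had SD 4.76.

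**3. Size of the extra noise.** Assume equal SDs at each timepoint. The SD of a change is SD × √(2(1 − r)). With r_w the correlation of pre with post at one visit and r_b the correlation of W0 with the later one-hour value,

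SD ratio = √((1 − r_b)/(1 − r_w)).

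The correlations below are assumptions.

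| r_w | r_b = 0.4 | r_b = 0.5 | r_b = 0.6 | r_b = 0.7 |
|---|---|---|---|---|
| 0.7 | 1.41 | 1.29 | 1.15 | 1.00 |
| 0.8 | 1.73 | 1.58 | 1.41 | 1.22 |
| 0.9 | 2.45 | 2.24 | 2.00 | 1.73 |

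The range is 1.0 to 2.4 (the largest entry is √6 = 2.449), or 1 to 6 in variance. At 0.8 and 0.5 the variance ratio is 0.5/0.2 = 2.5. With an assumed systolic SD of 15 mmHg, that is 15 × √0.4 = 9.5 mmHg for same-visit change against 15 × √1.0 = 15.0 mmHg for change from Week 0.

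**4. The same in terms of a comparison between arms.** With 89 per arm (Protocol 8.1), the difference in means detectable with 80% power is (1.96 + 0.84) × SD of change × √(2/89). At 0.8 and 0.5 this is 2.80 × 0.632 × 0.150 = 0.27 SD for same-visit change and 2.80 × 1.000 × 0.150 = 0.42 SD for change from Week 0. No such test is planned; the figures only express the loss of precision.

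**The case against.** The best case for the plan is that little is lost.

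- Raw values are tabulated at each timepoint by arm, and SAP 5.1.1 includes quartiles, minimum and maximum, so an extreme one-hour pressure would be visible.
- The randomised placebo arm removes drift common to both arms.
- Every reading is in Listing 16.2.10.
- Clinically evident reactions reach the adverse event tables by dose period, the seven-day solicited tables that include the injection day, and the monitoring board.
- SAP 7.3 declares its deletion openly and gives a data reason. An analysis plan cannot restore times that were not recorded.

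All of this stands. A reader might infer that immediate effects of doses 2 to 5 are badly measured or hidden. The documents do not support that: the readings are taken at every dose, tabulated and listed. Nor do they support saying that drift must bias the comparison with placebo. Common drift cancels; only drift that differs between arms would not.

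Three things remain. A minimum or maximum of raw values does not show whether that patient changed within the hour. Pairing from a listing leaves the reader to do by hand what one table would do. The solicited systemic reactions (fever, headache, fatigue, myalgia, nausea; Protocol 12.1.2) include no change in pulse or blood pressure, and the seven-day tables do not separate onset on the injection day.

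**Conclusion.** The concern holds as a weakness in summary. For doses 2 to 5 the stated baseline rule gives a one-hour change that includes drift and is usually noisier than the same-visit change. The paired SD, the distribution and the number of large acute shifts appear in no planned table. Dose 1 is unaffected on vital signs. The loss of the one-hour reaction analysis is a separate matter and applies to all five doses.

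The SD inflation of 1.0 to 2.4 rests wholly on assumed correlations and equal SDs. At the low end there is no loss, and less drift would be expected at Weeks 1 and 4 than at Week 24. The effect is on descriptive safety reporting only: no co-primary endpoint, hypothesis test or analysis population is touched. This is a cheap improvement.

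**What to change.** - In SAP 5.4.1, define a second baseline for the one-hour vital signs: the pre-dose value at the same visit. Add a table of one-hour minus same-visit pre-dose change for pulse, systolic and diastolic pressure, by dose and arm, beside Table 14.3.22.2, which stays as it is. The SD and quantiles of the paired change should be shown, with a count of patients beyond a shift size set before unblinding.
- As a substitute for the analysis dropped in SAP 7.3, tabulate solicited reactions with onset on the day of injection, by dose, intensity and arm. The adverse event listings carry start dates, and Protocol 12.2.2 makes diary Day 1 the day of administration. SAP 7.3 should also say whether reactions that staff recorded at one hour can be reported by visit without a clock time.

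The cost is two extra tables and a short definition, with no new data. The one limitation is that day of injection is coarser than one hour.

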5.2.5.2 Electrocardiogram (ECG)

For 12-lead ECG assessments variables collected, the frequencies of normal, Abnormal CS/N, Abnormal CS/AE, Abnormal NCS values will be reported by visit and treatment group (Statistical table 14.3.23).

All individual measurements will be provided in Listing 16.2.11.

5.2.5.3 Concomitant medications

Concomitant medications will be presented by ATC code and Preferred Name by treatment group (Statistical table 14.3.24)

Previous and concomitant medications for each patient will be reported in Listings 16.2.4.9.

5.3 Statistical/Analytical issues

5.3.1 Adjustments for Covariates

All models ANCOVA, MMRM, Logistic regression) will be adjusted on the minimization factors used for randomization (Ethnic (see section 9 Derived data) Origin, Age group, Presence or absence of renal involvement according to the BILAG at screening, With or without CS treatment at screening, With or without HCQ treatment at screening, With or without MMF treatment at screening).

In addition, MMRM will be adjusted on the baseline value.

For “Ethnic origin”, the reclassified values (see section 9 Derived data) will be used for primary analysis. The values from the eCRF will be used for sensitivity analysis. In the same way, for “Presence or absence of renal BILAG at screening”, the re-computed renal BILAG score derived in the statistics analysis datasets will

Statistical Analysis Plan

Study Name: IFN-K-002

SAP version & date: v4, 18/Jun/2018

be used for primary analysis. The values from the eCRF will be used as sensitivity analysis. (Statistical tables 14.2.3.1.4 & 14.2.3.2.3)

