Taking into account, that the number of patients will be considerable higher in this trial than in the study IFN-K-001, there is a high probability of a smaller standard deviation that could compensate for a possible smaller difference in mean changes. Therefore the sample size calculation gives a realistic estimate of the patients required for analysis to show a significant difference between active treatment and placebo.

Figure 1: Sample-size for different values of between group differences (expression of IFN-induced genes)

[figure not shown]
Assuming common SD=68 and a 0.05 two-sided type-one error rate

Assuming a BICLA response of 20.6% in the placebo group and 40.6% in IFN-K treated patients (i.e. an absolute difference of 20%) with 80 evaluable patients per group, there will be a 73% power to detect a difference of 20% in the BICLA response criterion.

The sample size needed to ensure a 80% power to the comparison of BICLA response rates between IFN-K and placebo for different response rates in the placebo arm and varying between

groups differences are presented in Figure 2. 97 evaluable patients per group would be needed for a power of 80% to detect a difference of 20% with a placebo response rate of 20.6%.

Figure 2: Sample-size for different values of between group differences (BICLA Response rate)

Assuming a power of 80% and a 0.05 two-sided type-one error rate

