13.9.2 Analysis of the Primary Efficacy Endpoint

The first co-primary efficacy endpoint - Percent change from baseline after 36 weeks of treatment in the expression of IFN-induced genes – will be analyzed using an ANCOVA.

The dependent variable will be the percentage change in the expression of IFN-induced genes and the treatment as independent variable. The minimization factors used for randomization - Race, Age range, Presence or absence of renal BILAG at screening, corticosteroid treatment, hydroxychloroquine treatment and MMF treatment at randomization - will be included as covariates.

The second co-primary efficacy endpoint - response to treatment according to BICLA - will be analyzed using a logistic regression using the response rate as dependent variable and treatment as independent variable, while adjusting for the minimization factors used for randomization.

First, the hypothesis with respect to the change from baseline in the expression of IFN-induced genes will be tested at an error probability of 5% for a 2-sided test. If and only if this Null-hypothesis can be rejected, the hypothesis with respect to the response to treatment according to BICLA will be tested also at an error probability of 5% for a 2-sided test.

The study will be considered as positive if a statistically significant better effect of IFN-K compared to placebo is observed on the neutralization of the IFN gene signature (i.e. the first co-primary endpoint) and if at least a trend favoring IFN-K is observed on the BICLA response (i.e. the second co-primary endpoint).

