2.3 Investigational plan

2.3.1 Study design and randomization

This is a Phase IIb, randomized, double-blind, placebo-controlled, multicenter study assessing intramuscular (IM) administration of IFN-K against an adjuvanted placebo. Study patients are enrolled into one of two treatment groups and allocated with a 1:1 randomization ratio to receive the study product: IFN-K or placebo as outlined below:

- Group 1: IFN-K emulsified in ISA 51 VG
- Group 2: placebo emulsified in ISA 51 VG

The study consists in a main study (double-blind) followed by an Extended Follow up Period (open label).

During the main study, each patient receives two injections of study product (corresponding to 240 mcg of IFN-K or placebo) at three visits during the Induction Period (at Week 0 [Visit 2], Week 1 [Visit 3], and Week 4 [Visit 4]). Each patient is administered one injection of study product (corresponding to 120 mcg of IFN-K or placebo) during the Maintenance Period (at Week 12 [Visit 6] and Week 24 [Visit 9]).

Statistical Analysis Plan

Study Name: IFN-K-002

SAP version & date: v4, 18/Jun/2018

The main study comprises a total of 12 visits occurring over a period of 40 weeks. The study is divided into four periods: a 4-week Screening Period that is performed to determine eligibility of the patients for randomization into the study, a 12-week Induction Period, a 12-week Maintenance Period and a 12-week Follow-up Period.

The Extended Follow up Period applies to all patients who have completed the main study. Then, when the results of the main study are available, only patients who have received IFN-K will continue the Extended Follow-up Period for up to 60 months (240 weeks) after Visit 12 (Week 36).

Treatment allocation at each site is performed using central randomization via an Interactive Web Response System (IWRS). The randomization algorithm was developed using a stochastic minimization with a minimization assignment probability parameter of 0.80. Randomization is minimized on:

- Ethnic Origin: Black, Asian, Caucasian/Hispanic, other
- Age: 18-40 or 41-65 years old
- Presence or absence of renal BILAG at screening
- With or without CS treatment at randomization
- With or without HCQ treatment at randomization
- With or without MMF treatment at randomization

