5.2.4 Efficacy analyses

5.2.4.1 Primary efficacy analysis

Descriptive statistics for IFN gene signature (first co-primary endpoint) at each visit and % of change from baseline by treatment group will be presented (Statistical tables 14.2.1.1.1 and 14.1.1.2).

The first co-primary efficacy endpoint - Percent of change from baseline after 36 weeks of treatment in the expression of IFN-induced genes – will be analyzed using an ANCOVA model (Statistical table 14.2.1.1.3).

The dependent variable will be the percentage of change from baseline in the expression of IFN-induced genes with the treatment as independent variable. The minimization factors used for randomization – Ethnic origin (see section 9 Derived data), Age group, Presence or absence of renal involvement according to BILAG at screening, corticosteroid treatment, hydroxychloroquine treatment and MMF treatment at screening - will be included as covariates. See section 5.3.2 for handling of missing data.

All IFN gene signature data will be listed in Listing 16.2.6.1.1.

Descriptive statistics for the response to treatment according to BICLA (second co-primary efficacy endpoint) at Week 36 will be presented by treatment group (Statistical table 14.2.1.2.1)

The second co-primary efficacy endpoint - response to treatment according to BICLA - will be analyzed using a logistic regression with the response rate as dependent variable and treatment as independent variable, while adjusting for the minimization factors used for randomization, as listed for the analysis of the first primary end-point (Statistical table 14.2.1.2.2).

Statistical Analysis Plan

Study Name: IFN-K-002

SAP version & date: v4, 18/Jun/2018

Response to treatment according to BICLA will be listed in Listing 16.2.6.1.2

First, the hypothesis with respect to the change from baseline in the expression of IFN-induced genes will be tested at an error probability of 5% for a 2-sided test. If and only if this Null-hypothesis can be rejected, the hypothesis with respect to the response to treatment according to BICLA will be tested also at an error probability of 5% for a 2-sided test.

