5.2.4.2 Sensitivity and supplementary analyses

The primary efficacy analysis will be repeated on the PP set as a supplementary analysis (Statistical tables 14.2.2.1.1 to 14.2.2.2.1).

It will be also repeated on the FAS population excluding patients with unblinding issue (see section 5.3.6) (Statistical tables 14.2.3.1.1 to 14.2.3.1.3 & 14.2.3.2.1 to 14.2.3.2.2.).

Then, the primary efficacy analysis will be repeated on the FAS for patients IFN-K treated with status of IFN α neutralizing antibodies (positive/negative) at Week 36 as dependent variable.

(Statistical tables 14.2.3.3.1 & 14.2.3.3.2).

Finally, the following analysis will be presented as a sensitivity analysis.

The time variation in IFN gene signature (first co-primary endpoint) will be modelled using a MMRM (mixed model for repeated measures) with random intercept, with percent change at each time point as dependent variable, and minimization factors used for randomization (Ethnic origin (see section 9 Derived data), Age group, Presence or absence of renal involvement according to BILAG at screening, corticosteroid treatment, hydroxychloroquine treatment and MMF treatment at screening, treatment and time as explanatory variables.

The treatment by time interaction will also be included in the model. (Statistical table 14.2.4).

Linearity will be checked graphically. In case of absence of evidence of non-linearity, time will be treated as continuous (variable calculated as the actual number of days since baseline). Otherwise, it will be treated as categorical. (Statistical figure 14.2.1)

Statistical Analysis Plan

Study Name: IFN-K-002

SAP version & date: v4, 18/Jun/2018

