7.2 Efficacy analysis

7.2.1 Primary efficacy analysis

A mixed model for repeated measures with random intercept using all measurements available (IFN gene signature/Score) until Week 36 has been added for the first co-primary endpoint to compute the estimate of the between group difference in change from baseline at week 36 as a sensitivity analysis.

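### The primary IFN-signature ANCOVA leaves out the Week 0 IFN score, which only the sensitivity MMRM adjusts for, and so gives up precision on the test that gates BICLA

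*SAP*

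**What the plan says.** SAP 5.2.4.1 defines the primary model for the first co-primary endpoint: "The dependent variable will be the percentage of change from baseline in the expression of IFN-induced genes with the treatment as independent variable". The only covariates are the six minimisation factors. Protocol 13.9.2 gives the same model, ending its list with "corticosteroid treatment, hydroxychloroquine treatment and MMF treatment at randomization - will be included as covariates".

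SAP 5.4.1 fixes the baseline for this endpoint: "For IFN gene signature, only Week 0 (visit 2) will be considered as baseline". The derivation table in SAP section 9 divides the change by that value.

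SAP 5.3.1 adjusts the ANCOVA, MMRM and logistic models for the minimisation factors and then adds, for one of them only, "In addition, MMRM will be adjusted on the baseline value". The MMRM is a sensitivity analysis (SAP 5.2.4.2 and 7.2.1). Its own variable list in 5.2.4.2 ends with "hydroxychloroquine treatment and MMF treatment at screening, treatment and time as explanatory variables" and does not name the baseline value.

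On timing of the treatment covariates, the minimisation list in SAP 2.3.1 has "With or without CS treatment at randomization", and likewise for hydroxychloroquine and MMF. Protocol 9.2.2 agrees. SAP 5.2.4.1, 5.2.4.2 and 5.3.1 take the same three factors at screening. SAP section 7 does not list this as a departure from the protocol.

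**The concern.** When the outcome is built from a baseline measurement, that measurement is the natural first covariate. If it predicts the change, including it lowers the residual variance without extra patients. Here it appears only in a model that does not carry the decision.

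The primary ANCOVA carries a good deal. BICLA is formally tested only if the IFN-signature null hypothesis is rejected (SAP 5.2.4.1 and 5.3.5), and the study can be called positive only if that test is significant. Protocol 13.1 also looks to a smaller SD as a cushion: "there is a high probability of a smaller standard deviation that could compensate for a possible smaller difference in mean changes". It links this to the larger sample, but a larger sample estimates the SD more precisely and does not systematically shrink it. Baseline adjustment can lower the residual SD.

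Some dependence of change on baseline is plausible. Protocol 5.4.3 reports that in the earlier study the fall in gene expression was larger in patients with the highest signature before immunisation. No correlation is given.

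**Working it through.** **Inputs** (protocol 13.1, SAP 2.3.2): 80 evaluable patients per arm, difference 32.6 points (from -22.6% to +10%), SD 68, two-sided 5% t-test. The correlation r between the Week 0 score and percent change within arms is not in the documents and is assumed, over the range 0 to 0.5.

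**Stated power.** Standard error = 68 × √(2/80) = 10.75. Noncentrality = 32.6 / 10.75 = 3.03. With 158 df, noncentral-t power is 85.4% (normal approximation 85.8%). The stated 85% reproduces and uses no baseline adjustment.

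**With the baseline term.** If the slope is the same in both arms, residual SD = 68 × √(1 − r²). The second power column uses a difference 5 points smaller (27.6), the situation for which protocol 13.1 wants a cushion.

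| r (assumed) | Residual SD | Power, difference 32.6 | Power, difference 27.6 |
|---|---|---|---|
| 0 | 68.0 | 85.4% | 72.3% |
| 0.1 | 67.7 | 85.7% | 72.7% |
| 0.2 | 66.6 | 86.8% | 74.0% |
| 0.3 | 64.9 | 88.5% | 76.3% |
| 0.4 | 62.3 | 90.8% | 79.5% |
| 0.5 | 58.9 | 93.6% | 83.8% |

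At 32.6 the gain runs from 0.3 point (r = 0.1) to 8.2 points (r = 0.5). At 27.6, r = 0.413 brings power back to 80%.

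**Degrees of freedom.** The full model has an intercept, treatment, 8 minimisation terms (3 for ethnic origin, 5 for the two-level factors) and baseline, so df = 160 − 11 = 149. This changes the figures by at most 0.1 point.

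**Type I error.** In simulations of 4,000 trials per setting, the rejection rate under no effect was 0.047 to 0.052 with or without the covariate. At r = 0 the cost is one degree of freedom.

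**Slope in one arm only.** If the correlation is r in the IFN-K arm and 0 in the placebo arm, a common-slope ANCOVA has residual SD = 68 × √(1 − r²/4):

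| r in IFN-K arm (assumed) | Residual SD | Power, difference 32.6 | Power, difference 27.6 |
|---|---|---|---|
| 0.3 | 67.2 | 86.2% | 73.3% |
| 0.5 | 65.8 | 87.5% | 75.0% |

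**The case against.** The SAP keeps the model prespecified in the protocol, that model meets its stated power, and a baseline-adjusted MMRM of the same endpoint is already planned. On this view the point is an optional efficiency gain. That the analysis is valid stands. The MMRM, however, would only show whether adjustment moves the estimate; it cannot open the gate to BICLA.

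The size of the gain is also open to challenge, and most of this stands:

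- r is unknown. Enrolling only signature-positive patients may narrow the baseline range and lower it.
- The minimisation factors may already absorb some of the baseline variation, so only the partial correlation counts.
- The earlier-study observation is listed among findings in patients receiving IFN-K. If the slope is confined to that arm, the gain at r = 0.5 falls from 8.2 to about 2 points, and r of about 0.41 no longer restores 80% at a difference of 27.6.
- Because baseline is the denominator of percent change, a linear term may fit poorly. The calculation credits only the linear part.

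On the MMRM list, 5.3.1 is the covariate section and can be read as completing 5.2.4.2. The gap there is one of clarity.

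On covariate timing, the SAP still calls these the factors used for randomisation, and SAP 5.2.1 tabulates them at randomisation, so the wording may simply be loose. The required prior duration of hydroxychloroquine and MMF, longer than the four-week screening window, makes a new start between the two visits unlikely; corticosteroid status is the one most likely to differ. The SAP does list tables with covariates as randomised (14.2.3.1.4 and 14.2.3.2.3), but 5.3.1 describes them only for ethnic origin and renal BILAG. The mismatch therefore remains, with little consequence for power.

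**Conclusion.** The concern holds. The test that decides whether BICLA is formally tested omits a baseline value that is already collected and that the SAP itself adjusts for in a sensitivity model. There is no bias, no inflation of type I error and no shortfall against the planned 85%. What is lost is precision. Under a common slope the loss is 0.3 point of power at r = 0.1, about 3 points at r = 0.3 and 8.2 points at r = 0.5; under a slope in the IFN-K arm only, it is about 2 points at r = 0.5. The true figure cannot be fixed from the documents. Since the downside is one degree of freedom, the change is worth making even if the gain turns out small. The mismatch between screening and randomisation status is a separate, minor inconsistency that SAP section 7 does not declare.

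**What to change.** Before database lock and unblinding:

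1. In SAP 5.2.4.1 and 5.3.1, add the Week 0 (Visit 2) IFN score as a covariate in the primary ANCOVA, and fix its scale in the SAP.
2. Name the same term in the MMRM variable list in SAP 5.2.4.2.
3. Record the addition in SAP 7.2.1 as a change from protocol 13.9.2. That section currently declares only the MMRM: "A mixed model for repeated measures with random intercept using all measurements available (IFN gene signature/Score) until Week 36 has been added".
4. Separately, in the ANCOVA, logistic and MMRM models, define corticosteroid, hydroxychloroquine and MMF status at randomisation, to match the minimisation and protocol 13.9.2.

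The cost is SAP wording, one model term and one line in section 7. No new data or patients are needed.
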